**Subjects must have S1 TG value  $\geq 425$  mg/dL and  $< 1800$  mg/dL before proceeding to S2.**

For subjects who required a Wash-Out Period and completed the Pre-Screening Visit, the following Screening Visit procedures will not be repeated: informed consent, full physical examination, height, TSH, HbA1c, and serology (HBV, HCV, and HIV). Updates, as needed, will be made to medical/surgical history, demographics, and concomitant medications.

The following procedures will be performed at the Screening Visit (up to Day -28):

- Obtain informed consent;
- Confirm eligibility based on inclusion/exclusion criteria;
- Obtain medical/surgical history and demographics;
- Obtain concomitant medications; including all anti-diabetes pharmacologic therapy for subjects with Type 2 diabetes;
- Perform full physical examination;
- Perform symptom-directed physical examination (only for subjects who required a Wash-Out Period and completed the full physical examination at the Pre-Screening Visit);
- Record vital signs, height, weight and BMI;
- Collect urine sample;
- Perform serum pregnancy test (for women of child-bearing potential only);
- Obtain blood sample for the following:
  - Safety chemistry panel, coagulation, and hematology;
  - TSH, HbA1c, and serology (HBV, HCV, and HIV); and
  - Fasting lipid panel;
- Perform 12-lead ECG;
- Explain importance of continued adherence to a stable, heart-healthy diet and limited alcohol intake; and
- Assess adverse events (AEs that occur prior to the first dose of study drug [Study Day 1] should be reported as an update to medical history as well as be reported on the appropriate adverse event eCRF) and concomitant medications.

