### 9.3.2 Analysis of Safety

Safety will be assessed using the SAS. The assessment of safety will include adverse events, clinical laboratory assessments, ECGs, physical examinations, and vital signs. In addition, the safety assessment will be based primarily on the frequency of new or worsening adverse events, laboratory abnormalities, and serious adverse events (SAEs). Other safety data will be summarized as appropriate.

AEs will be coded using the most recent version of the Medical Dictionary for Regulatory Activities (MedDRA). The summarization of AEs will include only treatment-emergent AEs (TEAEs), defined as AEs that begin or worsen after randomization and ingestion of the first dose of study drug. TEAEs and SAEs will be summarized by system organ class (SOC), severity, and relationship to study drug for each treatment group. Deaths, withdrawal from study treatment due to AEs, and withdrawal from the study due to AEs will each be summarized by treatment group.

Safety laboratory data will be summarized by treatment group at baseline, and at each post-baseline time point, if applicable, and change from baseline to End of Treatment (Week 12) or the ET Visit, if applicable. Baseline for safety laboratory data will be defined as the last pre-dose value (pre-dose Study Day 1/Visit T1 or prior). Frequency counts of new or worsening abnormalities will also be provided.

Vital signs data (value and change from baseline, where appropriate) will be summarized by treatment group at baseline and at each post-baseline time point. Baseline for vital signs data will be defined as the last pre-dose value (pre-dose Study Day 1/Visit T1 or prior). Abnormalities in ECGs and in PEs will be summarized.

All safety data will be listed.

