### 9.5 Handling of Missing Data

Missing values at baseline will not be imputed in any situation. For efficacy analyses, values missing post-randomization will be imputed using LOCF (unless otherwise specified); only post-randomization values on treatment will be used for imputation. For safety analyses, observed cases will be used.

Imputation will not be conducted for AEs missing severity or relationship to study medication. AEs missing severity will be excluded from summaries of AEs by severity. AEs missing relationship will be excluded from summaries of related AEs.

For AE start date, if only month and year are present, and they are the same month and year as the treatment start date, the day will be imputed by the treatment start day (and the AE will be considered treatment-emergent).

Rules for partial and missing dates for prior and concomitant medications are given in [Appendix 2](#).

Drug interruptions with partial start and/or stop dates will be assumed to be 1 day in length, and will be assumed to have occurred in the visit interval prior to when the interruption was collected (eg, if a drug interruption with partial dates was collected at the Week 10 visit, it is assumed that the interruption occurred between the previous visit [eg, Week 6] and the Week 10 visit).

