### 12.1 Adverse Events

AEs will be coded using Medical Dictionary for Regulatory Activities (MedDRA) version 19.1. All AE tables will be summarized for overall by treatment group and by stable statin use at baseline (according to the CRF) within treatment group. Except for the AE overview table and summaries of serious adverse events (SAEs) and AEs resulting in death (both of which will include all AEs), AE tables will only include summaries of treatment-emergent adverse events (TEAEs). A TEAE is defined as an AE with start date on or after the first dose date and less than 30 days after the last dose date. If AE start date is missing, the AE is assumed to be a TEAE. An AE overview table containing the frequency and percent of the following will be summarized by treatment group, and treatment group within each baseline statin (yes or no):

- Number of subjects with at least one TEAE, drug-related TEAE, SAE, drug-related SAE;
- Number of subjects who discontinued study treatment due to TEAE, drug-related TEAE, SAE, and drug-related SAE;
- Number of subjects who discontinued the study due to a TEAE; and
- Number of subjects who had a study treatment interruption due to a TEAE;
- Number of deaths and deaths due to a drug-related TEAE.

Additionally, the following will be summarized by treatment group, and treatment group within each stratum:

- TEAEs by system organ class (SOC) and preferred term (PT);
- TEAEs by descending PT ;
- TEAEs by SOC, PT, and maximum severity;
- Related TEAEs by SOC and PT;

- Related TEAEs by descending PT;
- SAEs by SOC and PT;
- Related SAEs by SOC and PT;
- TEAEs leading to treatment discontinuation by SOC and PT;
- Related TEAEs leading to treatment discontinuation by SOC and PT; and
- AEs that resulted in death by SOC and PT.

Summaries of SOC and PT will be sorted alphabetically by SOC and by decreasing frequency of PT in the total column for the gemcabene 600 mg group, followed by the 300 mg group, then placebo.

Note that the overview of AEs will be provided separately for the double-blind treatment period and follow-up period, to allow for a delivery of the double-blind data only during the database freeze.

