## Appendix 2. Prior and Concomitant Medications Date Imputation

Imputation Rules for Partial Dates (D = day, M = month, Y = year)			
Parameter	Missing	Additional Conditions	Imputation
Start date	D only	M and Y same as M and Y of first dose of study drug	Date of first dose of study drug
		M and/or Y not same as date of first dose of study drug	First day of month
	M and D	Y same as Y of first dose of study drug Y not same as Y of first dose of study drug	Date of first dose of study drug Use Jan 01 of Y
M, D, and Y	None - date completely missing		Day prior to date of first dose of study drug
	D only	M and Y same as M and Y of last dose of study drug	Date of last dose of study drug
		M and/or Y not same as date of last dose of study drug	Last day of month
M and D	Y same as Y of last dose of study drug		Date of last dose of study drug
	Y not same as Y of last dose of study drug		Use Dec 31 of Y
M, D, and Y	None - date completely missing and NOT ongoing		Date of last dose of study drug

Note: In all cases, if an estimated start date is after a complete stop date, use the first day of the stop date month.

Similarly, if the estimated stop date is before a complete or imputed start date, use the last day of the start date month.

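### The SAP's rules for incomplete AE start dates ignore the stop date, so an event recorded as over before first dose can be counted as treatment-emergent

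*SAP*

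**What the plan says.** **Partial start date (SAP 9.5).** The rule applies "if only month and year are present, and they are the same month and year as the treatment start date". The consequence is that "the day will be imputed by the treatment start day (and the AE will be considered treatment-emergent").

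**Missing start date (SAP 12.1).** "If AE start date is missing, the AE is assumed to be a TEAE". No date is imputed; only the classification is assumed.

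**TEAE definition.** SAP 12.1 defines a TEAE by onset alone: "an AE with start date on or after the first dose date and less than 30 days after the last dose date". Protocol 9.3.2 limits TEAEs to "AEs that begin or worsen after randomization and ingestion of the first dose of study drug". SAP 4.3, which lists changes from the protocol's analyses, declares no departure on this point.

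**Where a stop-date check does exist.** SAP Appendix 2 has this note: "In all cases, if an estimated start date is after a complete stop date, use the first day of the stop date month". The appendix title, and the pointer to it in SAP 9.5, confine it to prior and concomitant medications.

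**Pre-dose events in the AE data.** Protocol 6.2 (Pre-Screening) and 6.3.1 (Screening Visit 1) say that AEs before the first dose "should be reported as an update to medical history as well as be reported on the appropriate adverse event eCRF". SAP 12.1 plans a listing of all AEs, pre-treatment ones included, with those that are not treatment-emergent flagged.

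**The concern.** It is sensible to call an event treatment-emergent when its timing is unknown. Here the timing can be known. A recorded stop date before first dose shows that the event neither began nor worsened on study drug, yet both rules class it as a TEAE because they look only at the start field. The same event with a complete start date would be classed as pre-treatment, so a blank day field decides the classification.

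At stake are the TEAE counts in the overview table, the TEAE tables by system organ class and preferred term, the maximum-severity table, and the non-treatment-emergent flag in the AE listing. The partial-date rule can also leave records in the analysis data whose imputed start is later than their recorded stop. If that surfaces after unblinding, the records would have to be reclassified case by case with treatment known.

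**Working it through.** There is no figure in the plan to reproduce; this is a classification rule. It was checked by applying it to test events and by measuring how much pre-dose time it can reach.

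**1. Test events.** Assumed first dose 20 May 2017; event stopped 8 May 2017, so it was over 12 days before dosing.

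| Start date recorded | Rule | Imputed start | Class under SAP | Class with stop-date check |
|---|---|---|---|---|
| May 2017, day unknown | SAP 9.5 | 20 May (12 days after the stop) | TEAE | Pre-treatment |
| Missing | SAP 12.1 | none | TEAE | Pre-treatment |
| 5 May 2017 | SAP 12.1 definition | not needed | Not a TEAE | Not a TEAE |

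If the stop date is missing, or is on or after first dose, the first two rows stay TEAE with the check added.

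**2. Reach of the partial-date rule.** It needs the onset month and year to equal those of first dose. Assume first dose is equally likely on any day of 2017. If first dose falls on day d of the month, then min(L, d − 1) of the L preceding days lie in that month. Share = Σ min(L, d − 1) / (365 × L).

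- L = 14 (shortest screening): 3,850 / 5,110 = 75%
- L = 21: 4,893 / 7,665 = 64%
- L = 28 (longest screening): 5,348 / 10,220 = 52%
- L = 84 (8-week wash-out plus 28-day screening): 5,373 / 30,660 = 17.5%

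The wash-out part follows by difference. With 28-day screening, (5,373 − 5,348) / (365 × 56) = 25 / 20,440 = 0.1% of an 8-week wash-out lies in the first-dose month. This agrees with SAP Table 1: wash-out ends at Day −29, so it shares that month only when first dose falls on the 30th or 31st. With 14-day screening the figure is (5,373 − 3,850) / 20,440 = 7.5%. A 4-week wash-out halves the denominator and doubles both figures, to 0.2% and 14.9%. So the partial-date rule acts mainly on screening; only the missing-start rule spans the whole wash-out.

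**3. Which pre-dose events reach the AE form.**

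- All AEs: Protocol 6.2 and 6.3.1.
- SAEs only: Protocol 6.3.2, 6.3.3 and 8.1, and the Appendix A footnote to the AE row at Pre-Screening and Visit S1.

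On the second reading few non-serious events are exposed. Pre-dose SAEs could still enter the TEAE counts, but the SAE and death summaries do not depend on the TEAE flag, because SAP 12.1 puts all AEs in them.

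**4. Size per record.** With 30 subjects per arm, one subject whose only event at a given level is misclassified moves that arm's percentage by 1/30 = 3.3 points. AE tables are also split by stable statin use within arm, where denominators are smaller and one subject weighs more.

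**The case against.** The strongest defence is that treating uncertain onset as treatment-emergent is a common, conservative safety default. The rule is also a fallback: Protocol 10.1.1 and 10.1.5 have missing and inconsistent entries queried to sites, so few unresolved records should remain. Safety analysis is descriptive (SAP 12), with no between-arm test to distort. All of this stands and limits the size. It does not defend the rule for records where the stop date already settles the matter.

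A reader might infer more than the documents support:

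- *That every pre-dose day, including up to 8 weeks of wash-out, is exposed to both rules.* The partial-date rule is confined to the first-dose calendar month.
- *That every affected record acquires an impossible date.* SAP 12.1 assigns no date when the start is missing, so this happens only under SAP 9.5.
- *That one arm is favoured.* These events precede any study drug, so in expectation they add equally to all arms, raising rates and diluting differences. Chance imbalance is possible; systematic bias is not indicated.
- *That drug-related tables are distorted.* The causality guidance in Protocol 8.1.3 expects an event to follow dosing, so one that ended earlier should be rated unrelated. Entry to the related-TEAE tables is unlikely, though not excluded.

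**Conclusion.** The point holds, as a minor one. Two stated rules give a wrong classification whenever the start date is missing, or known only to the first-dose month, and the recorded stop date precedes first dose. That contradicts the protocol's TEAE definition, and the SAP declares no change to it. SAP 9.5 additionally produces a start after the stop.

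The expected consequence is a slight inflation of TEAE rates across all arms, at 3.3 points per affected subject in an arm of 30 when no other event at that level already counts. Efficacy results and the SAE and death tables are untouched. The number of such records is not given and is probably small; it depends on which of the protocol's two instructions on pre-dose AE recording the sites followed. The conclusion assumes that an AE stop date is collected on the eCRF, which is likely but not stated in either document. The calendar shares assume first doses spread evenly over the year.

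**What to change.** Add to SAP 9.5 and 12.1:

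*An AE whose start date is missing, or is known only to the month and year of first dose, is classed as treatment-emergent unless its recorded stop date (complete, or a month and year earlier than that of first dose) shows that it ended before first dose. In that case it is classed as pre-treatment, and no start date later than the stop date is imputed.*

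This retains the conservative default whenever the stop date is missing, uninformative, or on or after first dose. It serves a similar purpose to the medication check in Appendix 2 but is not the same: that check needs a complete stop date and moves the start to the first of the stop month, whereas this one changes the classification directly and also uses an earlier month and year.

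The cost is one sentence and one programming condition, to be settled before the Week 12 unblinding described in SAP 4.1. Confirm at the same time that the AE form captures a stop date, and reconcile the protocol sections on whether all pre-dose AEs or only SAEs are entered on it.

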## 9.6 Interim Analysis

There are no planned interim analyses.

## 9.7 Treatment Misallocations

In instances where treatment is improperly allocated to a patient for the entire study or at any point during the study, efficacy data will be summarized and analyzed as randomized. Safety data will be summarized conservatively by the highest dose of actual treatment received, where lowest to highest dose is: placebo, Gemcabene 300 mg, Gemcabene 600 mg. For example, if a subject is randomized to Gemcabene 300 mg treatment group and the subject incorrectly takes Gemcabene 600 mg at any point during the study, all safety data for that subject will be analyzed in the Gemcabene 600 mg treatment group.

## 9.8 Visit Windows

Visit windows will be used to classify scheduled (except the Follow-up Visit), unscheduled, and early termination (ET) visits according to Table 2 below to ensure that all visits have the potential to contribute to summaries. If 2 or more visits occur within the same analysis window, data from the visit closest to the target day will be used in summaries and/or analysis; if the visits are the same distance from the target day, data from the later date will be used. Data for laboratory and other parameters scheduled to be measured post-randomization at only the Week 12 or ET Visit (ie, fasting insulin, FPG, HbA1c, ANGPT4, adiponectin, lipoprotein size and particle number, waist circumference) will be summarized under the Week 12 Visit. If there is more than one value, the latest will be used. For efficacy, visits > 2 days after last dose will not be considered. For safety parameters analyzed by visit, visits > 5 days after last dose will not be considered.

**Table 2. Visit Windows for Assessments Done at Day 1, Weeks 2, 6, 10, and 12**

Visit	Target Study Day	Visit Window
Day 1/Visit T1	1	Day 1

**Table 2. Visit Windows for Assessments Done at Day 1, Weeks 2, 6, 10, and 12**

Visit	Target Study Day	Visit Window
Week 2/Visit T2	15	2, 29
Week 6/Visit T3	43	30, 57
Week 10/Visit T4	71	58, 78
Week 12/Visit T5	85	> 78

For parameters not measured at Week 2/Visit T2 and Week 10/Visit T4, the Visit Window for Week 6/Visit T3 is (2, 64) while Week 12/Visit T5 is > 64. For parameters not measured at Week 2/Visit T2 and Week 6/Visit T3, the Visit Windows for Week 10/Visit T4 and Week 12/Visit T5 are (2, 78) and > 78, respectively.

## 10 STATISTICAL ANALYSIS METHODS

### 10.1 Subject Disposition

The number of subjects screened, reasons for screen failure, and the number of subjects randomized will be summarized for all screened subjects. Number of subjects who complete and discontinue and reasons for study discontinuation that occur post-randomization will be summarized by randomized treatment group (ie, placebo, gemcabene 300 mg and gemcabene 600 mg) for all randomized subjects, the FAS, and the SAS. Reasons for discontinuation will be categorized using the reasons provided on the CRF (ie, AE, prohibited medication, non-compliance, withdrawal by subject, lost to follow-up, death, termination by sponsor, and other reasons). Additionally, protocol deviations will be listed for all randomized subjects.

### 10.2 Demographics and Baseline Characteristics

Demographic information will be summarized using descriptive statistics by randomized treatment group and overall for the FAS population. Additionally, demographic information will be presented by statin therapy (yes and no). The following characteristics will be summarized:

- Sex (Male, Female)
  - Menopausal Status for Females (post-menopausal or surgically sterile, pre-menopausal)
- Race (White, Black or African American, Asian, American Indian or Alaska Native, Native Hawaiian or Other Pacific Islander, Other)
- Ethnicity (Hispanic or Latino, Not Hispanic or Latino, Unknown)
- Age
- Age group (18-44, 45-64, >=65)
- Height
- Weight
- BMI, and
- BMI group (<30 kg/m^2, ≥ 30 kg/m^2)

where age will be computed for each subject using the following formula:

$$\text{Age} = \text{integer} ([\text{Screening Visit date} - \text{date of birth}] / 365.25),$$

and BMI will be calculated using the following formula:

$$\text{BMI} = (\text{body weight in kilograms})/(\text{height in meters})^2.$$

Pregnancy results will be listed for female subjects.

Baseline and stratification characteristics including the number and percentage of diabetic subjects, qualifying TG ( $<880 \text{ mg/dL}$ ,  $\geq 880 \text{ mg/dL}$ , randomized and actual) and subjects on and not on stable statin (randomized and actual) will be summarized. A subject on stable statin at baseline is defined as a subject with statin recorded on the Concomitant Medications CRF with a start date at least 12 weeks prior to first screening visit and a stop date on or after first dose (ie, medication stop date greater than or equal to day of first dose), or the medication is ongoing. Partial and missing dates will be imputed using rules in [Appendix 2](#).

Baseline primary, secondary, and exploratory endpoints will be summarized for the FAS by randomized treatment group and overall. Specifically, the following parameters will be summarized at baseline: lipids, apolipoproteins, lipoprotein size and particle number, inflammatory and other biomarkers, and visceral adiposity measures.

This table will be repeated by randomized baseline statin stratum (yes or no), baseline qualifying TG stratum, and diabetes status.

CI

For categorical parameters, denominators for percentages will be the number of subjects in the corresponding treatment group (eg, gemcabene 600 mg) with non-missing data for the parameter of interest.

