### 6.2.3 Exploratory Endpoints

The exploratory efficacy endpoints are as follows:

- CI [REDACTED]

- CI [REDACTED]
- [REDACTED]

Appendix 3 contains anatomical therapeutic chemical (ATC) categories and descriptions that will be used to identify anti-diabetes pharmacologic therapy for subjects. If an anti-diabetes pharmacologic therapy has a start date on or before first dose of study drug (ie, medication start date less than, or equal to day of first dose of study drug) and a stop date on or after first dose of study drug (ie, medication stop date greater than, or equal to day of first dose of study drug) it will be used in analysis. Partial and missing dates will be imputed using rules in Appendix 2.

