## **13.2 Prior and Concomitant Medications**

Prior and concomitant medications will be coded using the World Health Organization (WHO) Drug Dictionary version 01 Mar 2016. A prior medication is defined as a medication with a stop date prior to the date of the subject's first dose of study drug (ie, medication stop date less than date of first dose of study drug). A concomitant medication is defined as a medication with a start date on or before the date of the subject's last dose of study drug (ie, medication start date less than or equal to date of last dose of study drug) and a stop date on or after the date of the subject's first dose of study drug (ie, medication stop date  $\geq$  date of first dose of study drug);

thus, a medication that is ongoing at the time of the subject's first dose of study drug is considered concomitant. Partial and missing dates will be imputed using rules in [Appendix 2](#).

Prior and concomitant medications will be summarized in separate tables and listings. Medications taken within the period after last dose date and follow-up visit will not be summarized in the tables, but will be included in the concomitant medications listing. Medications will be summarized by ATC level 3 (level 3 indicates the therapeutic/pharmacologic subgroup) alphabetically and preferred name (decreasing frequency in the gemcabene 600mg column, then gemcabene 300 mg column within each ATC) by randomized treatment group for the SAS. At each level of summarization, subjects who report one or more medications within a given level (eg, ATC and preferred name) will only be counted once at that level.

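### SAP 10.2 can misclassify stable statin use: either an unknown or dosing-year-only start date can never pass the 12-week test, or ongoing statins skip that test, depending on how an unbracketed 'or' is read

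*SAP*

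**What the plan says.** SAP 10.2 summarizes stable-statin status both as randomized and as actual. The actual status comes from the Concomitant Medications CRF: a statin "with a start date at least 12 weeks prior to first screening visit" and a stop date on or after first dose, "or the medication is ongoing". No brackets show what the final clause attaches to. The section adds: "Partial and missing dates will be imputed using rules in" Appendix 2.

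Appendix 2 imputes a wholly missing start as "Day prior to date of first dose of study drug". When only the year is known and "Y same as Y of first dose of study drug" applies, the start becomes the date of first dose. A note adds that "if an estimated start date is after a complete stop date, use the first day of the stop date month".

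The SAP uses Appendix 2 in two other places, and both test timing against dosing rather than a look-back. Section 6.2.3 needs a "medication start date less than, or equal to day of first dose of study drug", and section 13.2 needs a "medication start date less than or equal to date of last dose of study drug"; each also needs a stop on or after first dose.

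The CRF-derived status then feeds SAP 12.1, which splits the adverse event tables by stable statin use at baseline according to the CRF. Protocol 4.1, inclusion criterion 3, admits statin users only if the statin was started at least 12 weeks before Screening.

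**The concern.** Imputing an unknown start to Day -1 or Day 1 is harmless when the question is whether a drug was in use around dosing. It decides the answer when the question is whether the drug began at least 12 weeks before screening. A long-term statin user whose start date was never retrieved could be reported as not on stable statin.

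The unbracketed clause raises a separate problem. Two programmers could each follow the text and produce different flags.

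Two outputs are at stake. The randomized-versus-actual table could show a mismatch that did not occur, and a statin user's adverse events could be filed under no statin. The split has a purpose: protocol 1.3 treats a sound safety profile alongside statins as necessary, and the adverse event tables are the only safety summaries in SAP section 12 specified by statin use. Laboratory, ECG, vital-sign and physical-examination summaries are by treatment group only.

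**Working it through.** The plan gives no figure of its own on this point, so the check is of the date rule.

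**Inputs.** The look-back is 12 weeks = 84 days (SAP 10.2). S1 falls 14 to 28 days before Day 1 (protocol 3.1 and 6.3). Pre-Screening, for wash-out subjects only, is 4 to 8 weeks before S1 (protocol 3.1). Imputed starts are Day 1 minus 1 (wholly missing) and Day 1 (dosing year only), from Appendix 2.

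**Two readings.**
- A: start AND (stop on or after first dose OR ongoing).
- B: (start AND stop on or after first dose) OR ongoing.

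**Reading A, date gap.** The latest passing start is S1 minus 84 days.
- S1 14 days before Day 1: 14 + 84 = 98 days before Day 1.
- S1 28 days before Day 1: 28 + 84 = 112 days before Day 1.
- Wholly missing start: short by 98 - 1 = 97 to 112 - 1 = 111 days.
- Dosing-year-only start: short by 98 to 112 days.

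If the first screening visit means Pre-Screening, it lies 14 + 28 = 42 to 28 + 56 = 84 days before Day 1. The cut-off is then 126 to 168 days before Day 1 and the gap only widens.

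**Does the Appendix 2 note rescue these cases?** It acts only when the imputed start is later than a complete stop date. Here the imputed start is never later than Day 1. A statin that meets the stop condition has a stop on or after Day 1 or is ongoing, so the note cannot apply. When the note does act, the statin stopped before first dose and fails the stop condition. Enumerating every first-dose date over two assumed calendar years (2017 and 2018), with six screening gaps and a range of stop dates, 0 of 1,533,000 cases in these two branches passed reading A.

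**When is the failure wrong?** A wholly missing start fails wrongly for any user who truly met the 12 weeks. A dosing-year start can truly lie 84 days before the visit only if that visit is on or after 1 January + 84 days = 26 March (25 March in a leap year). With S1 14 to 28 days before Day 1, in a non-leap year that means first dose on or after 9 to 23 April; before that, failing is correct.

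*Example:* first dose 1 September 2017, S1 28 days earlier on 4 August, cut-off 12 May. A true start of 2 January 2017 passes. Recorded only as 2017, it is imputed to 1 September and fails by 112 days.

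**Other branches.** First-of-month and 1 January imputation move the start earlier, so they never fail an eligible user. They can err the other way: with first dose 15 January 2018 and S1 28 days earlier, a true start of 1 December 2017 recorded only as 2017 becomes 1 January 2017 and passes.

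**Reading B.** All 8,760 enumerated ongoing-statin cases passed whatever the start date; a statin begun on Day 10 and still ongoing also counts as stable at baseline. Protocol 5.6.1 has subjects remain on background statins throughout, so ongoing is likely the usual entry. For those entries the imputation defect vanishes and the missing look-back replaces it. Only a statin with a recorded stop on or after first dose would still meet the imputation problem.

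**The case against.** The case for leaving the text alone has five parts.

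1. **Rarity.** Inclusion criterion 3 makes the site establish roughly when the statin began, and protocol 10.1.5 sends missing data back for query. This largely stands: few dates should remain unknown. It supplies no rule for those that do.

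2. **Reading B is available and mild.** A comma precedes the ongoing clause, so reading A is a judgement. Under B only a protocol deviation or an on-study start would be misclassed. That stands as a limit on size, but a baseline flag that admits a statin begun after first dose is still wrong, and the text does not choose.

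3. **Failing an undocumented start is conservative.** This is weak, because enrolment already required a 12-week history. An enrolled user with a lost date is more plausibly stable than not, and counting that subject as a non-user is not neutral in a safety split.

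4. **The outputs are descriptive and transparent.** This stands. Randomized and actual counts appear together and all adverse events are listed. SAP 12.1 is also not uniform: it refers to the CRF once, then to baseline statin and to stratum.

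5. **Any replacement rule trades one error for another.** Partly true. Use at screening does not prove 12 weeks of use, so the number classified that way should be shown.

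**Conclusion.** The rule needs correcting, but the correction is minor. On reading A, two imputation branches can never yield stable statin, by a margin of 97 to 112 days when S1 is the reference visit. On reading B, ongoing statins are not tested at all. Whichever is programmed, an ongoing statin meets one defect and not both.

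The reach is the actual stable-statin count in SAP 10.2 and the statin-split adverse event tables in 12.1. Each misclassified subject moves 1 of about 30 in an arm (1/30 = 3.3%) between statin groups. The documents do not give the number of such subjects, and it is not estimated here.

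A reader might infer three stronger things that the documents do not support:
- **That the primary analysis is affected.** SAP 11.1 says only baseline statin, yes or no, and 4.3 refers to the statin stratum for the secondary and exploratory models. Neither invokes the CRF-derived flag. The repeated baseline table in 10.2 uses the randomized stratum.
- **That many statin users are misfiled.** Only wholly missing or dosing-year-only starts that survive queries matter on reading A, and only deviations or on-study starts on reading B.
- **That the overall adverse event tables are wrong.** They do not depend on this flag.

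One assumption concerns Appendix 2, whose row labels are not intact in the available text. The wholly missing row that gives the day before first dose is read as a start-date row, because its stop-date counterpart is marked as not ongoing and imputes the last dose.

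**What to change.** In SAP 10.2:

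1. Bracket the definition as: start at least 12 weeks before the first screening visit AND (stop on or after first dose OR ongoing). State once whether the first screening visit is S1 or Pre-Screening for wash-out subjects, and use that visit throughout.
2. For this flag only, do not apply Appendix 2 start imputation when the start is wholly missing or known only to the dosing year. Query the site. If the start is still unknown, class the subject as on stable statin only if the statin was recorded as in use at that visit and the known date parts allow a start at least 84 days before it. For a year-only date, the visit must fall on or after 26 March of that year (25 March in a leap year). Otherwise class the subject as not on stable statin. Requiring use at that visit keeps out a statin begun on study.
3. Footnote, by treatment group, the number classified this way.

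The other Appendix 2 branches stay as they are, so the occasional wrong pass for a prior-year, year-only date remains.

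**Cost.** A few SAP sentences, one programming exception and one footnote, using the existing query process and the medication record already taken at Pre-Screening or S1 (protocol 6.2 and 6.3.1). No new assessments are needed. If the CRF does not show when a medication was first recorded, some source review is needed. A few subjects will be classed without a verified 12-week start.
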